7.0 Adverse Events

To comply with worldwide standards and guidelines on clinical investigation adverse event reporting, the Sponsor has adopted uniform and worldwide applicable standard definitions and reporting timelines to be used and adhered to by the investigators.

7.1 Definition

7.1.1 Adverse Event

An adverse event (AE) is any untoward medical occurrence, unintended disease or injury, or untoward clinical signs (including abnormal laboratory findings) in subjects, users or other persons, whether or not related to the medical device under investigation.

As part of ISO14155 Section 3.2, the Adverse Event definition has the following notes:

Note 1: This definition includes events related to the medical device under investigation or the comparator.

Note 2: This definition includes events related to the procedures involved.

Note 3: For users or other persons, this definition is restricted to events related to medical devices under investigation.

7.1.2 Serious Adverse Event

If the AE meets any of the criteria below, it is regarded as a serious adverse event (SAE).

- a) Led to a death,
- b) Led to a serious deterioration in health of the subject, that either resulted in
 1. a life-threatening illness or injury, or
 2. a permanent impairment of a body structure or a body function, or
 3. in-patient hospitalization or prolongation of existing hospitalization, or
 4. medical or surgical intervention to prevent life threatening illness or injury or permanent impairment to a body structure or a body function.
 5. chronic disease

This confidential document is the property of Abbott and shall not be reproduced, distributed, disclosed or used without the express written consent of Abbott

Post Market Surveillance Plan

- c) Led to fetal distress, fetal death or a congenital abnormality or birth defect.

Note: A planned hospitalization for a pre-existing condition, or a procedure required by the PMS plan without a serious deterioration in health, is not considered to be an SAE.

7.1.3 Device Deficiency

Device deficiency is defined as an inadequacy of a medical device related to its identity, quality, durability, reliability, safety or performance, such as malfunction, misuse or use error and inadequate labeling. This includes the failure of the device to meet its performance specifications or otherwise perform as intended. Note: performance specifications include all claims made in the labeling of the device.

7.2 Device Relationship

Determination of whether there is a reasonable possibility that the device under investigation caused or contributed to an AE is to be **determined by the Investigator** and recorded on the appropriate Case Report Form (CRF). Determination should be based on the assessment of temporal relationships, evidence of alternative etiology, medical/biologic plausibility and patient condition (pre-existing condition). If an AE or Device Deficiency is determined to be pump-related or possibly related, pump parameters should be reported in the appropriate CRF.

7.3 Adverse Event and Device Deficiency Reporting

7.3.1 Adverse Event Reporting

Safety surveillance and reporting starts as soon as the patient is enrolled in the post market surveillance. Safety surveillance and reporting will continue until sites perform the last follow-up visit, the subject is deceased, the subject concludes participation in the post market surveillance, or the subject withdraws from the post market surveillance. Sites will collect all adverse event data, including deaths and device deficiency data, throughout the period defined above and will report these events to the Sponsor on a CRF. Sites should update additional information regarding an adverse event on the appropriate CRF.

Unchanged, chronic, non-worsening or pre-existing conditions are not AEs and should not be reported.

The Sponsor will provide an offline form to allow the investigator to report SAEs in the event the entry cannot be made in the EDC. This does not replace the EDC reporting system. Sites must still enter all information in the EDC system as soon as feasible.

Non-cardiac related abnormal laboratory values will not be considered AEs unless:

1. the investigator determined that the value is clinically significant, OR
2. the abnormal lab value required intervention, OR
3. the abnormal lab value required subject withdrawal from the post market surveillance

This confidential document is the property of Abbott and shall not be reproduced, distributed, disclosed or used without the express written consent of Abbott

Post Market Surveillance Plan

All adverse events will be collected on each subject throughout the follow up period – until the subject reaches an outcome or withdraws or until the surveillance ends. Causes of death will be captured for all subjects who expire during follow up.

SAE Reporting

The investigator must report all SAEs to the Sponsor as soon as possible but no later than outlined below.

Clinical Site	Reporting timelines
All Sites	Sites must report SAEs to the Sponsor no later than 3 calendar days from the day the site personnel became aware of the event or as per the investigative site's local requirements, if the requirement is more stringent than those outlined.

Sites must record the date the site staff became aware that the event met the criteria of an SAE in the source document. The Investigator will further report the SAE to the local IRB according to the institution's IRB reporting requirements.

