- Abnormal pump parameters

Suspected pump thrombus should be accompanied by 1 or more of the following events or interventions:

- Treatment with intravenous anticoagulation (e.g., heparin), intravenous thrombolytics (e.g., tPA), or intravenous antiplatelet therapy (e.g., eptifibatide, tirofiban)
- Pump replacement
- Pump explant
- Urgent transplant (UNOS status 1A)
- Stroke
- Arterial non-CNS thromboembolism
- Death

Confirmed device thrombus is an event in which thrombus is confirmed by Abbott returned product analysis to be found within the blood contacting surfaces of device inflow cannula or outflow conduit or grafts. This can also be reported via direct visual inspection or by incontrovertible contrast radiographic evidence or by the absence of an appropriate Doppler flow signal that results in or could potentially induce circulatory failure or result in thromboembolism.

5. Hemolysis*

A plasma-free hemoglobin value that is greater than 40 mg/dl, concomitant with a rise in serum LDH above three times the upper limit of normal, in association with clinical signs associated with hemolysis (e.g., anemia, low hematocrit, hyperbilirubinemia) occurring after the first 72 hours post-implant.

*Hemolysis in the presence of worsening heart failure or inability to decompress the left ventricle or abnormal pump parameters should be reported as suspected device thrombosis, not as hemolysis

6. Hepatic Dysfunction

An increase in any two of the following hepatic laboratory values (total bilirubin, aspartate aminotransferase/AST and alanine aminotransferase/ALT) to a level greater than three times the upper limit of normal for the hospital, beyond 14 days post-implant (or if hepatic dysfunction is the primary cause of death).

7. Hypertension

Blood pressure elevation of a mean arterial pressure greater than 110 mm Hg, despite anti-hypertensive therapy.

This confidential document is the property of Abbott and shall not be reproduced, distributed, disclosed or used without the express written consent of Abbott

Post Market Surveillance Plan

8. Major Infection

A clinical infection accompanied by pain, fever, drainage and/or leukocytosis that is treated by anti-microbial agents (non-prophylactic). A positive culture from the infected site or organ should be present unless strong clinical evidence indicates the need for treatment despite negative cultures. The general categories of infection are listed below:

Localized Non-Device Infection

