This confidential document is the property of Abbott and shall not be reproduced, distributed, disclosed or used without the express written consent of Abbott

Post Market Surveillance Plan

Acute Renal Dysfunction

Abnormal kidney function requiring dialysis (including hemofiltration) in Subjects who did not require this procedure prior to implant, or a rise in serum creatinine of greater than 3 times baseline or greater than 5 mg/dL sustained for over 48 hours.

Chronic Renal Dysfunction

An increase in serum creatinine of 2 mg/dl or greater above baseline, or requirement for hemodialysis sustained for at least 90 days.

13. Respiratory Failure

Impairment of respiratory function requiring reintubation, tracheostomy or (the inability to discontinue ventilatory support within six days (144 hours) post-VAD implant. This excludes intubation for reoperation or temporary intubation for diagnostic or therapeutic procedures.

14. Right Heart Failure

Symptoms and signs of persistent right ventricular dysfunction requiring RVAD implantation or requiring inhaled nitric oxide or inotropic therapy for a duration of more than 1 week at any time after LVAD implantation.

15. Arterial Non-CNS Thromboembolism

An acute systemic arterial perfusion deficit in any non-cerebrovascular organ system due to thromboembolism confirmed by one or more of the following:

- Standard clinical and laboratory testing
- Operative findings
- Autopsy findings

This definition excludes neurological events.

16. Venous Thromboembolism Event

Evidence of venous thromboembolic event (e.g. deep vein thrombosis, pulmonary embolism) by standard clinical and laboratory testing.

17. Wound Dehiscence

Disruption of the exposed surfaces of a surgical incision, excluding infectious etiology, and requiring surgical repair.

18. Other

An event that causes clinically relevant changes in the Subject's health (e.g. cancer).

Post Market Surveillance Plan

MODIFIED RANKIN SCORE

Score	Definition
0	No observed neurological symptoms
1	No significant neurological disability despite symptoms; able to carry out all usual duties and activities
2	Slight neurological disability; unable to carry out all previous activities, but able to look after own affairs without assistance
3	Moderate neurological disability; requiring some help, but able to walk without assistance
4	Moderate severe neurological disability; unable to walk without assistance and unable to attend to own bodily needs without assistance

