#### 1.4.2 Primary Safety Endpoint

Primary safety endpoint is measured by the cumulative occurrence of all adverse events defined in Appendix II of the CIP.

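### No rule says whether the section 7.3.1 laboratory exception or the Appendix II hepatic and renal definitions prevail, so primary safety events can go unreported

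*Protocol*

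**What the plan says.** Protocol 7.1.1 defines an adverse event broadly and includes "untoward clinical signs (including abnormal laboratory findings) in subjects, users or other persons". Section 7.3.1 then narrows this: "Non-cardiac related abnormal laboratory values will not be considered AEs unless" at least one of three conditions is met. They are:

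- "the investigator determined that the value is clinically significant, OR"
- "the abnormal lab value required intervention, OR"
- "the abnormal lab value required subject withdrawal from the post market surveillance"

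Neither the term for non-cardiac values nor clinical significance is defined.

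Appendix II defines the named events. Item 6, hepatic dysfunction, begins "An increase in any two of the following hepatic laboratory values" and requires two of bilirubin, AST and ALT above three times the hospital's upper limit of normal more than 14 days after implant. The only alternative is hepatic dysfunction as the primary cause of death. Item 12 gives acute and chronic renal dysfunction a dialysis limb and a creatinine limb each; the chronic creatinine limb reads "An increase in serum creatinine of 2 mg/dl or greater above baseline".

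SAP 1.4.2 states: "Primary safety endpoint is measured by the cumulative occurrence of all adverse events defined in Appendix II of the CIP". SAP 2.2.4 and Protocol 8.2.2 agree, and report the endpoint as percent of subjects and events per patient-year.

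**The concern.** Sites report under section 7.3.1, but the endpoint is counted under Appendix II. The first puts an investigator's judgement in front of definitions that, for these events, contain none. A result can meet the hepatic thresholds, be annotated as not clinically significant and settle untreated. Under 7.3.1 it is then not an adverse event; under Appendix II it belongs in the primary safety endpoint.

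Any such omission can only lower the reported rate. It can also differ between the roughly four sites, because the key terms are undefined. The SAP counts reported events and has no step that derives hepatic or renal events from laboratory data. Neither document describes independent event adjudication.

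**Working it through.** This is mainly a comparison of texts. The plan states no figure to reproduce: about 30 subjects is a feasibility estimate, and the SAP says that no endpoint is powered.

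**Step 1. Each Appendix II limb against the 7.3.1 exception**

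| Limb | Basis | Exposed to the exception? |
|---|---|---|
| Hepatic, laboratory | Two of three tests above 3 times the upper limit, after day 14 | Yes |
| Hepatic, cause of death | Death | No, not a bare laboratory value |
| Acute renal, dialysis | Dialysis or hemofiltration | No, an intervention |
| Acute renal, creatinine | Above 3 times baseline or above 5 mg/dL, for over 48 hours | Yes |
| Chronic renal, hemodialysis | Hemodialysis | No, an intervention |
| Chronic renal, creatinine | Rise of at least 2 mg/dL over baseline | Yes |

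Elsewhere Appendix II states clinical input where it wants it: hemolysis needs associated clinical signs, and peri-operative infarction needs clinical suspicion. The three exposed limbs have no comparable condition, so 7.3.1 adds one.

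**Step 2. Search for a precedence rule**

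Protocol 2.1 and 4.0 point to Appendix II for the adverse event definitions. Section 7.3.1 does not mention Appendix II, and Appendix II does not mention the exception. Neither document says which governs when both apply.

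**Step 3. Scale**

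Inputs: N = 30 (Protocol 3.0) and the two-year HeartMate 3 rates in Appendix IV, from the CE Mark study to MOMENTUM 3. Expected subjects = N × rate.

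- Hepatic: 30 × 0.020 = 0.60, to 30 × 0.049 = 1.47.
- Renal: 30 × 0.10 = 3.00, to 30 × 0.142 = 4.26. These are upper limits on what is exposed, because the rates are for renal dysfunction as a whole and dialysis cases pass the exception.
- One subject: 1/30 = 3.3 percentage points.

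**Step 4. Illustration under assumed loss**

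The documents give no share of events that the exception would remove. Assume shares f of 0, 25% and 50%. The chance that no subject is recorded is (1 − p(1 − f))^30.

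| Event and rate p | f = 0 | f = 25% | f = 50% |
|---|---|---|---|
| Hepatic 2.0% | 0.545 | 0.635 | 0.740 |
| Hepatic 4.9% | 0.222 | 0.325 | 0.475 |
| Renal 10% | 0.042 | 0.096 | 0.215 |
| Renal 14.2% | 0.010 | 0.034 | 0.110 |

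With so few hepatic events expected, one omission can decide whether any is reported. One subject is still small against sampling error: the exact 95% interval for 4 of 30 (13.3%) runs from 3.8% to 30.7%.

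**The case against.** The best defence is that Appendix II already controls. Protocol 2.1 and 4.0 and the endpoint wording all refer to it, and 7.3.1 itself requires all adverse events to be collected. On that reading the exception screens only stray laboratory abnormalities that match no named event. This is a natural reading, and it means that the text is ambiguous and gives no express permission to omit endpoint events. It does not settle the matter, because 7.3.1 is the section that sites follow when reporting and it contains no such limit.

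Three further points stand in part:

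- The exception covers only non-cardiac values, so hepatic or renal changes attributed to heart failure may fall outside it. Values this extreme will also often be judged significant or be treated. Both points reduce the likely loss, but the documents do not allow the reduction to be measured.
- General controls exist: annotation of out-of-range results where applicable (11.3), monitoring (10.4), EDC checks with sponsor review (11.0) and a Data Management Plan (11.2). None is stated to test Appendix II thresholds. The Data Management Plan is a separate document, so a check there cannot be ruled out.
- No endpoint is powered and there is no success criterion, so no formal decision turns on a missed case. That limits the importance of the point.

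A reader might also infer that investigators may hold back laboratory results. They may not: AST, ALT, bilirubin and creatinine are scheduled at baseline and at every follow-up visit whatever their adverse event status. The exception governs only whether a value is reported as an adverse event.

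**Conclusion.** The two rules overlap for the hepatic laboratory definition and the two creatinine-only renal limbs, and no precedence is stated. Read literally, section 7.3.1 allows an event that belongs in the primary safety endpoint to go unreported as an adverse event. The direction of any bias is downward, and it may vary by site.

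Its size cannot be derived. The figures of 0.6 to 1.5 hepatic subjects and at most 3.0 to 4.3 renal subjects of 30 show scale only; they assume that the Appendix IV rates carry over and that 30 subjects are enrolled. They should not be read as an estimate of missed events.

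A reader might also conclude that the resulting rates could not be compared with Appendix IV. The documents do not support this: they do not say whether the cited studies used a similar laboratory exception.

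This is a cheap improvement to the plan and does not undermine the study.

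**What to change.** Add one sentence to Protocol 7.3.1: the laboratory exception does not apply to values that meet an Appendix II definition, and these are always reported as adverse events.

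As a partial backstop, before database lock, compare all collected AST, ALT, bilirubin and creatinine values with the Appendix II thresholds and query any subject with no matching event. Include unscheduled and out-of-window values, because Protocol 8.6 and SAP 2.8 exclude out-of-window data from analysis and the check would otherwise miss them. The check can be set out in the Data Management Plan and cited in SAP 2.2.4.

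The check has limits. It needs each hospital's upper limit of normal, which Protocol Tables 1 and 3 do not list. Visits at months 1, 3, 6, 12 and 24 cannot confirm a 48-hour creatinine rise between visits. It therefore supports the added sentence and cannot replace it.

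The cost is one protocol sentence, one programmed listing and collection of the reference limits if the CRFs do not already hold them. The downside is a few more queries and possibly slightly higher reported rates.

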7.3.2 Device Deficiency Reporting

Device deficiencies should be reported on the appropriate CRF form only if they are associated with any adverse events.

The investigator should report device deficiencies associated with AEs to the Sponsor as soon as possible but no later than outlined below.

Clinical Sites	Reporting timelines
All Sites	Device deficiencies must be reported to the Sponsor no later than 3 calendar days from the day the site personnel became aware of the event or as per the investigative site's local requirements, if the requirement is more stringent than those outlined.

Device deficiencies should be reported to the IRB per the investigative site's local requirements.

An offline form will be made available to allow the investigator to report device deficiencies, if the entry cannot be made in the EDC system. This does not replace the EDC reporting system. All information must still be entered in the EDC system as soon as feasible.

In case a device deficiency occurred before the patient ID number has been assigned, the device deficiency should be reported to the Sponsor via the offline reporting form.

Post Market Surveillance Plan

Irrespective of the device deficiency requirement per this investigation, the site must submit all device deficiencies to Sponsor Product Performance Group in order to be captured in the Sponsor complaints database.

7.3.3 Adverse Event and Device Deficiency Reporting to Country Regulatory Authorities by the Sponsor

The Sponsor will report SAEs and reportable device deficiencies to the country regulatory authority, per local requirements. All reportable events will be reported to the Competent Authority per the applicable regulations by the Product Performance Group (PPG).

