8.2.3.5 Device Malfunctions

All suspected HM3 device malfunctions will be reported. Data on device malfunctions will be analyzed and tables will be created that report the following:

- The component of the device involved
- Days to the malfunction
- Action taken in response to the malfunction
- Reoperations due to malfunction
- Death due to malfunction

Note: Device malfunctions will be collected under the general category of Device Deficiencies (section 7.1.3) and the term is defined further in Appendix II.

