5	Severe neurological disability; bedridden, incontinent and requiring constant nursing care and attention as a result of a neurological deficit
6	Death

Post Market Surveillance Plan

DEVICE MALFUNCTIONS

A Device Malfunction occurs when any component of the MCS system ceased to operate to its designated performance specifications or otherwise fails to perform as intended. Performance specifications include all claims made in the Instructions for Use.

Internal Component Malfunction: Malfunction of any device system component that is implanted within the patient. A malfunction to these components may require further surgery to repair or replace.

External Component Malfunction: Malfunction of a device system component that is used external to the patient and can be replaced or repaired without the need for further surgery.

Post Market Surveillance Plan

NEW YORK HEART ASSOCIATION (NYHA) CLASSIFICATION

NYHA Classification	Definition
I	Cardiac disease without resulting limitations of physical activity. Ordinary physical activity does not cause undue fatigue, palpitations, dyspnea or anginal pain.
II	Cardiac disease resulting in slight limitation of physical activity. Subjects are comfortable at rest. Ordinary physical activity results in fatigue, palpitation, dyspnea or anginal pain.
IIIA	Cardiac disease resulting in marked limitations of physical activity. Subjects are comfortable at rest. Less than ordinary physical activity causes fatigue, palpitation, dyspnea, or anginal pain.
IIIB	Cardiac disease resulting in marked limitations of physical activity. Subjects are comfortable at rest. Mild physical activity causes fatigue, palpitation, dyspnea, or anginal pain.
IV*	Cardiac disease resulting in inability to carry on any physical activity without discomfort. Symptoms of cardiac insufficiency or of the anginal syndrome may be present even at rest. If any physical activity is undertaken, discomfort is increased.

*For all post-enrollment NYHA assessments, any patient who is inotrope dependent will be considered NYHA Class IV.

Post Market Surveillance Plan

INTERMACS PROFILE

INTERMACS Profile*	Definition
1	Critical cardiogenic shock describes a patient who is “crashing and burning”, in which a patient has life-threatening hypotension and rapidly escalating inotropic pressor support, with critical organ hypoperfusion often confirmed by worsening acidosis and lactate levels.

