To date, there have been no adverse effects related to this issue; however, it may lead to frequent advisory alarms that may need to be silenced. In the notification to investigators, the Sponsor provided recommendations for managing patients with advisory alarms. The Sponsor has received acknowledgment forms from all investigators indicating that they were made aware of the issue and the associated recommendations.

Post Market Surveillance Plan

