#### 2.2.5.5 Device Malfunction

Percent of patients with suspected HM3 device malfunctions and frequency of all suspected malfunctions will be reported by components of HM3 involved. Additionally, days to the malfunction, reoperations or death due to malfunction and actions taken in response to malfunction will be reported.

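### The malfunction endpoint promises all suspected HM3 malfunctions, but the CRF rule admits only device deficiencies associated with an adverse event

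*Protocol*

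**What the plan says.** **Endpoint.** Protocol 8.2.3.5 states: "All suspected HM3 device malfunctions will be reported". It then lists tables by component, days to malfunction, action taken, and resulting reoperation or death. SAP 2.2.5.5 commits to the same scope: "Percent of patients with suspected HM3 device malfunctions and frequency of all suspected malfunctions will be reported by components of HM3 involved". SAP 1.4.3 lists malfunction as a secondary endpoint, covering both frequency and consequences.

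**Route.** The note in Protocol 8.2.3.5 says: "Device malfunctions will be collected under the general category of Device Deficiencies". Table 5 footnote 5 likewise places malfunction inside device deficiency.

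**Capture rule.** Protocol 7.3.2 says: "Device deficiencies should be reported on the appropriate CRF form only if they are associated with any adverse events". Table 5 footnote 4 points to 7.3.2 and also restricts capture, but to deficiencies that lead to an adverse event, which is a narrower, causal condition.

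**Other routes.** Protocol 7.3.1 has a general sentence: "Sites will collect all adverse event data, including deaths and device deficiency data, throughout the period defined above", with these events to be reported on a CRF. The end of 7.3.2 requires sites to send every deficiency to the sponsor's product performance group for the complaints database, whatever this study itself requires.

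**The concern.** The endpoint covers all suspected malfunctions. The study form through which they are to be collected takes only those tied to an adverse event. Tables built from that form would carry a label wider than their content.

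This matters because, for a descriptive endpoint, the count is the whole result. Device malfunction is among the outcomes in Protocol 4.0 and the secondary endpoints in SAP 1.4.3. Any shortfall makes the device look more reliable. Protocol 15.1 names a lower risk of device malfunction as an anticipated benefit over the HeartMate II, and SAP 2.4 allows interim descriptive reports for regulatory or reimbursement use. A reader of such a report would take the malfunction figure as complete.

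**Working it through.** The documents give no malfunction figure to reproduce, so the check compares texts first and then works out the direction of the error.

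**1. Does either definition already require an adverse event?** No.
- Protocol 7.1.3, on deficiency: "This includes the failure of the device to meet its performance specifications or otherwise perform as intended".
- Appendix II, on malfunction: "A Device Malfunction occurs when any component of the MCS system ceased to operate to its designated performance specifications". It also covers external components that can be repaired or replaced without surgery, which can plausibly fail without harm.

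**2. Does the capture rule apply to malfunctions?** Yes. The 8.2.3.5 note and footnote 5 both place malfunctions within device deficiencies, and 7.3.2 limits which deficiencies go on the CRF.

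**3. Can the excluded class occur?** Yes. Appendix IV says of the HM3 driveline communication fault: "To date, there have been no adverse effects related to this issue". Its known consequence was advisory alarms. Manufacturing was changed for later lots, so this shows only that such events exist, not how often to expect them here.

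**4. Does another route fill the tables?** None is stated. The complaints route is described as separate from the study's own requirement. Neither document names it as a source for the malfunction tables or describes linking complaint records to key-coded subjects.

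**5. Direction.** Let M be all suspected malfunctions and A those associated with an adverse event. A is a subset of M, so:
- frequency: the number in A is at most the number in M;
- patients: those with at least one event in A are at most those with at least one event in M.

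Both measures fall or stay equal. The ratio of reported to true lies between 0 and 1 for each.

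**6. Size.** With a denominator of 30 (Protocol 3.0 and 5.6, approximate), each patient whose only malfunctions are free of adverse events lowers the percent by 1/30 = 0.033, or 3.3 percentage points.

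For the frequency, let f be the share of malfunctions without an adverse event. The documents give no value, so the values below are assumptions. The reported count is (1 − f) of the true count. A malfunction that leads to death is adverse-event-associated and stays in, so the fraction of recorded malfunctions leading to death is multiplied by 1/(1 − f).

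| f (assumed) | Reported count / true count | Inflation of fraction leading to death |
|---|---|---|
| 0.25 | 0.75 | 1.33 |
| 0.50 | 0.50 | 2.0 |
| 0.75 | 0.25 | 4.0 |

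The filter therefore lowers the frequency and, wherever a malfunction leads to death, makes the recorded malfunctions look more lethal than they are.

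**7. Which measure suffers more?** This cannot be determined, because it depends on how events cluster. Two invented cases show it:
- Ten patients have one adverse-event-free malfunction each, and two patients have ten adverse-event malfunctions each. Frequency ratio 20/30 = 0.67; patient ratio 2/12 = 0.17.
- Ten patients have one malfunction of each kind. Frequency ratio 10/20 = 0.50; patient ratio 10/10 = 1.00.

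**The case against.** **The collection rule is unclear rather than plainly restricted.** Protocol 7.3.1 can be read as putting all deficiency data on a CRF. Protocol 7.2 asks for pump parameters on the CRF for a pump-related adverse event or device deficiency, as if a deficiency could stand alone. The 8.2.3.5 note points to 7.1.3, which has no restriction. The CRFs are under separate cover (Appendix V) and could not be checked. In part this stands: the conclusion must be conditional on a CRF that follows 7.3.2. It does not remove the conflict. The specific rule in 7.3.2, repeated in footnote 4, narrows the general sentence in 7.3.1, and 7.2 only adds pump parameters. If 7.3.1 is meant literally, it contradicts 7.3.2.

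**The split is deliberate.** The plan sends adverse-event-associated deficiencies to the study CRF and all deficiencies to complaints handling. That is a legitimate design. It leaves the endpoint label inaccurate unless the complaints records are used for the tables, and nothing says they will be.

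**Little is at stake.** SAP 1.4.3 states that no endpoint is powered, and SAP 2.6 sets no success criterion. Reoperations, rehospitalizations and outcomes are collected separately (Protocol 6.4.2, 6.4.3, 6.5). The broad adverse event definition in 7.1.1 may also bring more malfunctions onto the CRF. All of this stands and limits the gap mainly to malfunctions without clinical consequence.

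**A plan amendment may not be needed.** Protocol 8.8 lets major changes to the analysis plan be made by SAP amendment, so naming a data source could be done there alone. This stands for that step. The conflicting collection wording in the protocol would remain.

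**Conclusion.** The concern holds. The protocol and SAP promise all suspected malfunctions, while the stated study collection rule admits only those associated with an adverse event. Tables built from a CRF that follows 7.3.2 would omit the rest.

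The direction is certain: frequency and percent of patients can only be understated or unchanged. The total size is unknown, because the documents give neither a malfunction rate nor the share with an adverse event. The only firm figure is 3.3 percentage points per affected patient at the approximate planned size of 30.

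The conclusion rests on two assumptions: that the unseen CRF follows 7.3.2, and that the tables draw on the CRF alone. It should be fixed because it affects the accuracy of a reported secondary endpoint. It does not mean that the sponsor would miss a safety signal, since every deficiency must still be submitted to it.

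**What to change.** **Preferred.** Delete the adverse-event condition from Protocol 7.3.2 and reword Table 5 footnote 4 to match. Record every suspected malfunction on the CRF with a yes/no flag for an associated adverse event. Report the total and the adverse-event-associated subset, each as frequency and percent of patients.

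**Alternatives.**
- (a) Keep the restricted CRF and name the complaints records, reconciled to enrolled subjects, as the data source in SAP 2.2.5.5.
- (b) Keep the restricted CRF and retitle the endpoint and tables in Protocol 8.2.3.5 and SAP 2.2.5.5 as malfunctions associated with an adverse event.

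**With any option.** Use one threshold in 7.3.2 and footnote 4 (association or causation), and state in 7.3.1 which deficiency data go on a CRF.

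**Cost.** The protocol edits need a plan amendment with IRB notification or approval, documented before implementation (Protocol 10.2 and 12.1). The preferred option adds little data entry, since sites must already submit every deficiency to the sponsor. Option (a) needs a SAP amendment and a procedure that links complaint records to key-coded subjects (Protocol 11.1). Option (b) needs the SAP wording changed as well as the protocol.
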